8.3.7 Adverse events based on examinations and tests

The results from the Clinical Study Protocol mandated laboratory tests and vital signs will be summarised in the CSR. Deterioration as compared to baseline in protocol-mandated laboratory values/vital signs should therefore only be reported as AEs if they fulfil any of the SAE criteria or are the reason for discontinuation of treatment with the investigational product.

If deterioration in a laboratory value/vital sign is associated with clinical signs and symptoms, the sign or symptom will be reported as an AE and the associated laboratory result/vital sign will be considered as additional information. Wherever possible the reporting Investigator uses the clinical, rather than the laboratory term (e.g., anaemia versus low haemoglobin value). In the absence of clinical signs or symptoms, clinically relevant deteriorations in non-mandated parameters should be reported as AE(s).

Any new or aggravated clinically relevant abnormal medical finding at a physical examination as compared with the baseline assessment will be reported as an AE.

When collecting AEs, the recording of diagnoses is preferred, when possible, to recording a list of signs and symptoms. Asthma symptoms or signs, such as wheeze, cough, chest tightness, dyspnea, breathlessness and phlegm, will be recorded as AEs only when:

- The sign or symptom is serious according to definitions, see [Appendix B](#)
- The patient discontinues IP due to the sign or symptom
- The sign or symptom is new to the patient or not consistent with the patient's preexisting asthma history (defined as within 1 year of Visit 1) as judged by the Investigator.

Asthma exacerbation should be recorded as an AE or SAE only if it fulfills any of the above criteria.

8.3.8 Adverse Events of Special Interest

An adverse event of special interest (AESI) is an event of scientific and medical interest towards improving the understanding of the IP. An AESI may be serious or non-serious. For this study, AESIs include:

- Anaphylactic reactions
- Immune complex disease (Type III hypersensitivity reactions)
- Malignancy
- Helminth infections
- Severe infections which are defined as:

- SAEs or
- Requiring treatment with systemic antiviral medications, intravenous antibiotics or medications for helminth parasitic infection or
- Requiring a permanent discontinuation of study drug
- Injection site reactions
- Opportunistic infections
- Guillain Barre Syndrome

8.3.9 Hy's law

Cases where a subject shows elevation in liver biochemistry may require further evaluation and occurrences of AST or ALT $\geq 3 \times \text{ULN}$ together with total bilirubin $\geq 2 \times \text{ULN}$ may need to be reported as SAEs. Please refer to Appendix E 4 for further instruction on cases of increases in liver biochemistry and evaluation of Hy's Law.

8.4 Safety reporting and medical management

8.4.1 Reporting of serious adverse events

All SAEs must be reported, whether or not considered causally related to the IP, or to the study procedure(s). All SAEs will be recorded in the CRF.

If any SAE occurs in the course of the study, then Investigators or other site personnel must inform the appropriate AstraZeneca representatives within one day i.e., immediately but **no later than 24 hours** of when he or she becomes aware of it.

The designated AstraZeneca representative will work with the Investigator to ensure that all the necessary information is provided to the AstraZeneca Patient Safety data entry site **within 1 calendar day** of initial receipt for fatal and life threatening events **and within 5 calendar days** of initial receipt for all other SAEs.

For fatal or life-threatening adverse events where important or relevant information is missing, active follow-up will be undertaken immediately. Investigators or other site personnel will inform AstraZeneca representatives of any follow-up information on a previously reported SAE within one calendar day i.e., immediately but **no later than 24 hours** of when he or she becomes aware of it.

Once the Investigators or other site personnel indicate an AE is serious in the WBDC system, an automated email alert is sent to the designated AstraZeneca representative(s).

If the WBDC system is not available, then the Investigator or other study site staff must report a SAE to the appropriate AstraZeneca representative(s) by telephone.

The AstraZeneca representative(s) will advise the Investigator/study site staff how to proceed.

The reference document for definition of expectedness/listedness is the Investigator's Brochure for the AstraZeneca IP.

8.4.2 Pregnancy

All pregnancies and outcomes of pregnancy should be reported to AstraZeneca except if the pregnancy is discovered before the study subject has received any study drug. If a pregnancy is reported, the investigator should inform the sponsor within 24 hours of learning of the pregnancy.

Abnormal pregnancy outcomes (eg, spontaneous abortion, foetal death, stillbirth, congenital anomalies, ectopic pregnancy) are considered SAEs.

8.4.2.1 Maternal exposure

If a subject becomes pregnant during the course of the study, IP should be discontinued immediately.

Pregnancy itself is not regarded as an adverse event unless there is a suspicion that the IP under study may have interfered with the effectiveness of a contraceptive medication. Congenital abnormalities/birth defects and spontaneous miscarriages should be reported and handled as SAEs. Elective abortions without complications should not be handled as AEs. The outcome of all pregnancies (spontaneous miscarriage, elective termination, ectopic pregnancy, normal birth or congenital abnormality) should be followed up and documented even if the subject was discontinued from the study.

If any pregnancy occurs in the course of the study, then the Investigator or other site personnel must inform the appropriate AstraZeneca representatives within 1 day i.e., immediately but **no later than 24 hours** of when he or she becomes aware of it.

The designated AstraZeneca representative works with the Investigator to ensure that all relevant information is provided to the AstraZeneca Patient Safety data entry site within 1 or 5 calendar days for SAEs (see Section 8.4.1) and within 30 days for all other pregnancies.

The same timelines apply when outcome information is available.

The PREGREP module in the CRF is used to report the pregnancy and the PREGOUT is used to report the outcome of the pregnancy.

8.4.2.2 Paternal exposure

Pregnancy of the subject's partners will not be considered an AE. However, the outcome of all pregnancies (spontaneous miscarriage, elective termination, ectopic pregnancy, normal birth, or congenital abnormality) should be followed up and documented in the Pregnancy Report Form for conceptions occurring from the date of the first administration of IP until 16 weeks (5 half-lives) after the last administration of IP. Consent from the partner must be obtained before the Pregnancy Report Form is completed.

8.4.3 Overdose

A dose in excess of 280 mg administered within a 2-week period is considered an overdose.

There is currently no specific treatment in the event of overdose of IP and possible symptoms of an overdose are not established.

An overdose with associated AEs is recorded as the AE diagnosis/symptoms on the relevant AE modules in the CRF and on the Overdose CRF module.

An overdose without associated symptoms is only reported on the Overdose CRF module.

If an overdose on an AstraZeneca study drug occurs in the course of the study, then the Investigator or other site personnel inform appropriate AstraZeneca representatives immediately, or **no later than 24 hours** of when he or she becomes aware of it.

The designated AstraZeneca representative works with the Investigator to ensure that all relevant information is provided to the AstraZeneca Patient Safety data entry site.

For overdoses associated with a SAE, the standard reporting timelines apply, see Section 8.3.2. For other overdoses, reporting must occur within 30 days.

8.4.4 Medication error

If a medication error occurs in the course of the study, then the Investigator or other site personnel informs the appropriate AstraZeneca representatives within 1 day i.e., immediately but **no later than 24 hours** of when he or she becomes aware of it.

The designated AstraZeneca representative works with the Investigator to ensure that all relevant information is completed within 1 (Initial Fatal/Life-Threatening or follow-up Fatal/Life-Threatening) or 5 (other serious initial and follow-up) calendar days if there is an SAE associated with the medication error (see Section 8.3.2) and within 30 days for all other medication errors.

The definition of a Medication Error can be found in Appendix B 8.

8.4.5 Management of IP-related toxicities

Appropriate drugs, such as epinephrine, H1 and H2 antihistamines, and corticosteroids, as well as medical equipment to treat acute anaphylactic reactions, must be immediately available when IP is being administered. Study site personnel must be trained to recognize and treat anaphylaxis (Lieberman et al. 2010). Details on anaphylaxis management are provided in Appendix G .

Anaphylaxis will be defined as a serious reaction that is rapid in onset and may cause death (Sampson et al. 2006). Anaphylaxis typically manifest as 1 of 3 clinical scenarios:

1. The acute onset of a reaction (minutes to hours) with involvement of the skin, mucosal tissue or both and at least one of the following: a) respiratory compromise; or b) reduced blood pressure or symptoms of end-organ dysfunction

2. Two or more of the following that occur rapidly after exposure: involvement of the skin/mucosal tissue, respiratory compromise, reduced blood pressure or associated symptoms and/or persistent gastrointestinal symptoms
3. Reduced blood pressure after exposure.

Subjects will have had a pre-assessment (i.e., vital signs and lung function) prior to IP administration. At Visits 3 and 5, subjects should be observed for a minimum of 2 hours after IP administration for the appearance of any acute drug reactions. For the remaining visits involving IP administration, subjects will be observed for a minimum of 1 hour after IP administration for any such reaction.

If an anaphylactic reaction occurs, a blood sample will be drawn from the subject as soon as possible after the event, at 60 minutes \pm 30 minutes after the event, and at discharge for analysis of serum tryptase. The sample will be tested at the local lab or central lab where applicable.

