halfway into the SC tissue. The IP will be slowly injected (at least 5 second duration is recommended) into the SC tissue using gentle pressure. The area should not be massaged after injection. It is advised that the site of injection of IP be rotated such that the subject receives IP at a different anatomical site at each treatment visit. In cases when rotation of the injection site is not feasible and/or the subject prefers not to rotate injection sites, the reason for not rotating the injection site should be documented in the source documents. The suggested injection site rotation sequence is presented below in [Figure 2](#).

Figure 2 Suggested schema of Rotation of Injection Sites

Subjects should be observed for a minimum of 2 hours after administration of the first two IP administrations for the appearance of any acute drug reactions. For the remaining doses, subjects will be observed for a minimum of 1 hour after IP administration for any such reaction.

If any of the following should occur, the IP should not be administered:

- The subject received allergen immunotherapy injection on the same day as scheduled IP administration.
- The subject has an intercurrent illness that in the opinion of the investigator and/or medical monitor may compromise the safety of the subject in the study (e.g., viral illnesses).
- The subject is febrile ($\geq 38^{\circ}\text{C}$; $\geq 100.4^{\circ}\text{F}$) within 72 hours prior to IP administration.

The visit should be rescheduled within the allowed visit window and IP should be administered at that visit. If this is not possible the IP administration should be skipped. If a subject skips 2 consecutive IP administrations, the AZ study physician should be contacted to discuss further participation.

If the subject reports an injection site reaction, the investigator or qualified designee will complete the AE eCRF page and an additional eCRF page with questions about the injection site reaction.

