Appendix I Changes Related to COVID-19 Pandemic

Please Note: Changes below should only be implemented during the COVID-19 pandemic and if allowable by local/regional guidelines.

I 1 Home Visits to Replace On-Site Visits (where applicable)

Due to local travel restrictions and/or site restrictions, subjects may not wish to or may not be able to go to the study site for study visits and related procedures. If an on-site visit is not possible, it is recommended to have a home visit with home administration of IP by a qualified HCP (up to Visit 16) or without administration of IP for EOT Visit and Visits 18 and 19, provided this is acceptable within local regulation/guidance. Additional information related to the visit can be obtained remotely by phone call and/or video conference. This is to ensure safety of the study subjects and minimum disruption to IP administration that may occur during the COVID-19 pandemic.

Study assessments, where possible to be performed at home, should be conducted according to the SoA. At minimum, during home visit the qualified HCP is expected to:

- Collect information on healthcare resources utilization
- Perform a physical examination
- Collect vital signs
- Collect adverse events
- Collect information on asthma exacerbation
- Review concomitant medications
- If possible, collect blood sample according to the SoA
- Conduct urine pregnancy test (dipstick), prior to IP administration, if applicable
- eDiary data completion/review
- Administer IP
- Observe the subject for one hour after IP administration for the signs or symptoms of any acute drug reactions
- Document the visit

Please refer to the separate IP Home (or Alternative Site) Administration Instructions for more information.

I 2 Visits at an Alternate Location (where applicable)

Study visits including administration of IP and study assessments according to the SoA can take place at an alternative location away from infection risk zones, or closer to the subject's home, provided this is acceptable within local regulation/guidance.

Please refer to the separate IP Home (or Alternative Site) Administration Instructions for more information.

I 3 Remote Visits to Replace On-Site Visits (where applicable)

During the COVID-19 pandemic, on-site visits may be replaced by a remote visit (phone call and/or video conference) if subjects cannot attend the visits at the study site, at an alternate site or have home visits and if allowed by local/regional guidelines.

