3.3 Derivation of safety variables

3.3.1 Exposure to IP and treatment compliance

Extent of exposure to IP is defined as the number of days between the date of first dose of IP and the date of last dose of IP inclusive plus the number of days allowance for the dosing interval specified in [Section 2.1.5](#), that is:

$$\text{Extent of exposure (days)} = \text{minimum (date of last dose of IP + 33 days; date of death; date of study withdrawal)} - \text{date of first dose of IP} + 1$$

This calculation does not consider any gaps in exposure caused by the subject missing one or more intermediate scheduled 4-weekly doses. Such cases will be identified in the CSR if they occur, but will not explicitly be accounted for in any analysis.

The total subject-years exposure for a treatment group will be derived as the sum of the individual subject extents of exposure (days) for that treatment group and divided by 365.25.

Treatment compliance will be calculated as follows:

$$\text{Treatment compliance (\%)} = \left[\frac{\text{Total number of actual dosing occasions}}{\text{total number of expected dosing occasions}} \right] \times 100\%$$

In order to allow for subjects who discontinue IP early in the compliance calculation, the number of expected dosing occasions will be calculated as the number of scheduled dosing visits up to and including the last available dosing visit for that subject.

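### Protocol Section 8.4.5 ties the 2-hour post-dose watch to Visits 3 and 5, so a second dose delayed past Visit 5 gets 1 hour there but 2 hours under Section 6.2

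*Protocol*

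**What the plan says.** Two sections of the protocol set the observation time after an injection.

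- **Section 6.2 (Dose Administration)** goes by dose order: "Subjects should be observed for a minimum of 2 hours after administration of the first two IP administrations". It continues: "For the remaining doses, subjects will be observed for a minimum of 1 hour after IP administration for any such reaction".
- **Section 8.4.5 (Management of IP-related toxicities)** goes by visit number: "At Visits 3 and 5, subjects should be observed for a minimum of 2 hours after IP administration". It continues: "For the remaining visits involving IP administration, subjects will be observed for a minimum of 1 hour after IP administration".

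Section 6.2 also says what happens when a subject cannot be dosed on the day, for example because of recent fever or an intercurrent illness. The visit is moved within its window, and then: "If this is not possible the IP administration should be skipped". One skipped dose does not end treatment. The next step comes only after two in a row: "If a subject skips 2 consecutive IP administrations, the AZ study physician should be contacted to discuss further participation".

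SAP Section 3.3.1 expects missed doses too. It says that the exposure calculation ignores "any gaps in exposure caused by the subject missing one or more intermediate scheduled 4-weekly doses".

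**The concern.** Both sections exist to catch acute drug reactions, and both put the longer watch on early exposure. Section 6.2 follows the exposure itself. Section 8.4.5 follows the calendar, so it drops the second hour when the second exposure comes late. Nothing in the protocol suggests that a delayed second dose is safer than one given on time.

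The second hour is not idle. Section 8.4.5 describes anaphylaxis as developing over minutes to hours. Anaphylactic reactions are an adverse event of special interest (Section 8.3.8), and a reaction to study drug that needs epinephrine is a criterion for stopping it (Section 7.1).

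Staff looking for instructions on reactions would turn to Section 8.4.5. A site that releases a subject after 1 hour at Visit 6 complies with that section and breaches Section 6.2 on the same dose. At stake are one hour of safety observation and the consistency of the instructions, not the trial's statistical conclusions.

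**Working it through.** The plan states no figure to reproduce. The check sets the two rules against the dosing schedule.

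**Inputs**

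- Dosing visits (Protocol Table 2): Visit 3 (Week 0), none at Visit 4 (Week 2), then Visits 5 to 16 (Weeks 4 to 48). That is 1 + 12 = 13 scheduled doses.
- Window at Visits 5, 6 and 7 (Table 2): ±5 days.
- Observation rules: Sections 6.2 and 8.4.5.
- Skipping rule: Section 6.2.

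**Minimum observation for the first two doses received**

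| Pattern | First two doses at | Section 6.2 | Section 8.4.5 | Gap |
|---|---|---|---|---|
| On schedule | Visits 3, 5 | 2 + 2 = 4 h | 2 + 2 = 4 h | 0 h |
| Visit 5 moved within ±5 days | Visits 3, 5 | 2 + 2 = 4 h | 2 + 2 = 4 h | 0 h |
| Visit 5 dose skipped | Visits 3, 6 | 2 + 2 = 4 h | 2 + 1 = 3 h | 1 h |
| Visit 5 and 6 doses skipped | Visits 3, 7 | 2 + 2 = 4 h | 2 + 1 = 3 h | 1 h |

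The rules therefore differ only when the Visit 5 dose is missed altogether. The difference is then 1 hour at one dose, out of at most 13 − 1 = 12 doses in a subject with that single skip. From the third dose received, both sections give 1 hour.

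**Home dosing**

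Appendix I 1 of the protocol lists one hour of observation after home dosing, with no exception for early doses. The list is introduced as a floor: "At minimum, during home visit the qualified HCP is expected to". Whether a second dose could have been given at home under that appendix depends on dates. Assume that the last subject reaches Week 52 on 31 December 2020, the end of the quarter planned in the synopsis, on the target day:

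- Randomization: 31 December 2020 − 364 days = 2 January 2020.
- Latest Visit 5: + 28 + 5 days = 4 February 2020.
- Latest Visit 6: + 56 + 5 days = 3 March 2020.
- Latest Visit 7: + 84 + 5 days = 31 March 2020.

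All three precede protocol version 5.0, dated 14 May 2020 in the SAP amendment history. On the planned dates, almost no second dose would fall under the home-visit rule, so home doses are left out of the count.

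**The case against.** The strongest reply is that the protocol, read as a whole, already gives the right answer. Both times are minimums, so 2 hours at the second dose satisfies both sections. Section 6.2 governs dose administration, and its dose-order rule sits just above its skipping rule, so a site that skips Visit 5 has the correct instruction in front of it. The visit numbers in Section 8.4.5 are most likely shorthand for the first two scheduled doses. This all stands, and it is why the point is minor. It does not remove the inconsistency: Section 8.4.5 gives 1 hour as the minimum for every other dosing visit, and a site that follows it does what it is told.

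A second reply is that the case is rare. Few conditions bar a dose, and moving the visit within ±5 days usually keeps the dose at Visit 5. This stands too. SAP Section 3.3.1 deals with missed doses in general and gives no rate for Visit 5.

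A third reply is that the remedy comes late. On the dates worked out above, essentially every second dose would have been given before any amendment after version 5.0. For this trial the practical gain would then be close to nil, and the value of the edit lies in a consistent protocol and in any later protocol that reuses the text. The mismatch itself is not affected.

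Finally, at least 1 hour of observation applies under either section, and Section 8.4.5 requires emergency drugs, equipment and trained staff whenever study drug is given.

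**Conclusion.** The concern holds as a minor internal inconsistency in a safety procedure. When the Visit 5 dose is skipped and dosing continues, the second dose carries a 2-hour minimum under Section 6.2 and a 1-hour minimum under Section 8.4.5. Subjects dosed on schedule, or rescheduled within the window, are unaffected.

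The conclusion rests on the wording of the two sections and the schedule in Table 2, with no numerical assumption. The documents do not give the number of subjects affected; that it is small is a judgement. The planned-date assumption bears only on home dosing and on how much an amendment could still achieve. Sample size, power, type I error and the efficacy analyses do not change.

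**What to change.** Reword Section 8.4.5 to go by dose order, and leave Section 6.2 as it is. For example: *observe for at least 2 hours after each of the first two doses the subject actually receives, regardless of visit, and for at least 1 hour after every later dose*. The two sections then agree under every pattern of skipped doses.

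A matching phrase in the home-visit list of Appendix I 1 (two hours if the dose is one of the subject's first two) would be tidy but is optional. The list is already a minimum, and the separate home-administration instructions, which are not available for review, may cover the point.

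The cost is a wording change at the next amendment, plus one extra hour on site at one visit for any subject whose second dose is delayed. On the planned dates few or no such visits would remain in this trial.
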